2.5 Rationale and significance

As detailed above, a previously-demonstrated correlation between the density of CRC-infiltrating effector T cells and long-term outcomes [11, 12] has been established. In our preclinical ex vivo studies performed using explants of resected metastatic CRC, the combination of IFN α with nonselective or COX2-selective inhibitors of prostaglandin synthesis resulted in elevated production of the effector T cell-attracting chemokines CXCL10 and CCL5. This was associated with concomitant suppression of the intratumoral expression of CCL22, a T_{reg}-attracting chemokine [63, 64]. However, in a subset of patients, the optimal results, particularly with regard to CCL5 induction, required additional stimulation by a third agent, a TLR3 Ligand. NCT01545141 demonstrated the safety of the CKM regimen administered over 5 days, without the emergence of new adverse effects or with compromise of surgical outcomes. However, the brief course, limited patient numbers, and lack of pre-treatment biopsies did not allow for an objective estimate of clinical efficacy nor did it allow for a robust evaluation of the impact of this CKM regimen on the tumor microenvironment. If solid evidence of a beneficial biologic effect on colorectal were demonstrated, this would strongly support further investigation, as a self-standing treatment in adjuvant settings or in combination with checkpoint blockade, vaccination or adoptive T cell transfer, which all depend on the presence of T cells in tumor microenvironments (or the ability of T cells to enter tumors).

We seek to establish the immunologic impact of an abridged 3 day course of a chemokine regimen, consisting of Interferon Alpha-2b, celecoxib, and rintatolimod, administered in repeated sessions over 3 weeks. A 3 day regimen will be used preferentially over the 5 day regimen due to concerns of chronic toxicity with multiple cycles and also for ease of implementation and participant scheduling. We further seek to evaluate clinical activity and to confirm the observed safety profile with repeated dosing. We hypothesize that the proposed chemokine modulation treatment in recurrent/metastatic CRC patients may increase the density of tumor infiltrating lymphocytes (TILS) and provide anti-cancer benefit.

Treatment with serial liver biopsies will allow us the comparative analysis of the effect of chemokine modulation on the local recruitment of effector-type T cells **and** the de-recruitment of T_{reg} within affected tumor tissues; helping us to determine the “preferred” chemokine-modulating regimen for subsequent extended studies. Such prospective studies will focus on using combinations of chemokine modulation and cancer vaccines or immune checkpoint inhibitors in patients with CRC. We have, for example, recently observed that α DC1, a new type of DC vaccine [65, 66] is particularly effective in inducing the effector pathway of T cells differentiation. This was manifested by the induction of tumor-killing function and the induction of effector-type chemokine receptors (CXCR3 and CCR5) [65, 67]. Combining the α DC1 vaccine to a safe, tolerable and efficacious CKM regimen may hold promise for patients with poor prognostic CRC.

PROTOCOL TITLE: Phase 2A Study Evaluating a Chemokine-Modulatory Regimen in Patients with Colorectal Cancer Metastatic to the Liver

Pre-clinical data similarly demonstrates significant benefit with the addition of anti-PD-1 therapy to a CKM regimen, making this another natural combination.

3 INCLUSION AND EXCLUSION CRITERIA

3.1 Inclusion Criteria:

To be included in this study, participants must meet the following criteria:

1. Recurrent and/or metastatic unresectable colorectal cancer with hepatic metastases.
2. Hepatic metastases present which are amenable to biopsy.
3. Prior treatment with, contra-indication to or refusal of a fluoropyrimidine, irinotecan, oxaliplatin and an anti-EGFR targeted therapy (if RAS wt), as well as a PD-1 or PD-L1 targeted drug if MSI-H/dMMR.
4. No chemotherapy, radiotherapy, major surgery, or biologic therapy within 3 weeks of protocol treatment.
5. An ECOG performance status of 0, 1, or 2. Refer to Appendix C.
6. Have measurable disease per RECIST 1.1 criteria present.
7. Ability to swallow and retain oral medications.
8. Participants of child-bearing potential must agree to use adequate contraceptive methods (e.g., hormonal or barrier method of birth control; abstinence) prior to study entry. Should a woman become pregnant or suspect she is pregnant while she or her partner is participating in this study, she should inform her treating physician immediately.
9. Age equal to 18 years or older.
10. Must have normal organ and marrow function as defined below:
 - Platelet \geq 75,000/ μ L
 - Hemoglobin \geq 9 g/dL
 - Hematocrit \geq 27%
 - Absolute Neutrophil Count (ANC) \geq 1500/ μ L
 - Creatinine \leq institutional upper limit of normal (ULN)

OR

- Creatinine clearance \geq 50 mL/min for patients with creatinine levels greater than ULN (refer to Appendix I for Cockcroft-Gault Equation)
- Total bilirubin \leq 1.5 X institutional ULN or for patients with known Gilbert's Syndrome total bilirubin \leq 3 x ULN
- AST (SGOT) and ALT(SGPT) \leq 2.5 X institutional ULN
- Plasma amylase and lipase \leq 1.5 X institutional ULN.

PROTOCOL TITLE: Phase 2A Study Evaluating a Chemokine-Modulatory Regimen in Patients with Colorectal Cancer Metastatic to the Liver

11. Participant or legal representative must understand the investigational nature of this study and sign an Independent Ethics Committee/Institutional Review Board approved written informed consent form prior to receiving any study related procedure.

Please refer to Appendix D for the Investigator Study Eligibility Verification Form: Inclusion Criteria.

3.2 Exclusion criteria

Participants will be excluded from the study for the following:

1. Patients currently treated with systemic immunosuppressive agents, including steroids, are ineligible until 3 weeks after removal from immunosuppressive treatment.
2. Patients with active autoimmune disease requiring ongoing immunosuppressive therapy or, history of transplantation.
3. Patients who are pregnant or nursing. Women of childbearing potential (WOCBP) will have to undergo a urine pregnancy test as part of screening.
4. Untreated CNS metastases.
5. Cardiac risk factors including:
 - Patients experiencing cardiac event(s) (acute coronary syndrome, myocardial infarction, or ischemia) within 3 months of signing consent
 - Patients with a New York Heart Association classification of III or IV (Appendix A)
6. History of upper gastrointestinal ulceration, upper gastrointestinal bleeding, or upper gastrointestinal perforation within the past 3 years. Patients with ulceration, bleeding or perforation in the lower bowel are not excluded.
7. Prior allergic reaction or hypersensitivity to celecoxib, NSAIDs, or any study agents which would prevent completion of protocol-therapy.
8. Patients are ineligible if they plan on regular use of NSAIDs at any dose more than 2 times per week (on average) or aspirin at more than 325 mg at least three times per week, on average. Low-dose aspirin not exceeding 100 mg/day is permitted. Patients who agree to stop regular NSAIDs or higher dose aspirin are eligible and no wash out period is required.
9. Received an investigational agent within 30 days prior to enrollment.
10. Unwilling or unable to follow protocol requirements.
11. Patients with known serious mood disorders.
12. Any additional condition which in the Investigator's opinion deems the participant an unsuitable candidate to receive the study drugs

Please refer to Appendix E for the Investigator Study Eligibility Verification Form: Exclusion Criteria.

3.3 Inclusion of Women and Minorities

Both men and women and members of all races and ethnic groups are eligible for this study.

PROTOCOL TITLE: Phase 2A Study Evaluating a Chemokine-Modulatory Regimen in Patients with Colorectal Cancer Metastatic to the Liver

4 LOCAL AND STUDY-WIDE NUMBER OF SUBJECTS

Estimated number of RPCI subjects: The number of subjects required for this study is approximately 15 (12 evaluable for the primary endpoint), but will depend upon the number of additional accruals required to replace subjects who fail to meet the criteria for efficacy evaluation. Accordingly, the subject accruals cannot be known ahead of time but can only be estimated. All participants will be enrolled from RPCI. There will be no network site participation.

4.1 Target Accrual

Approximately 15 patients (12 evaluable for the primary endpoint) will be needed to estimate the biologic impact of this regimen and establish a preliminary estimate of efficacy. Total accrual time is expected to take approximately 48 months.

5 LOCAL AND STUDY-WIDE RECRUITMENT METHODS

5.1 Recruitment

Potential participants will be identified and recruited during scheduled visits to the RPCI Gastrointestinal (GI) Center. Non-investigator RPCI physicians and community physicians may also refer potential subjects to the investigator for evaluation. There will be no “cold calling”. Informed consent will be obtained on all subjects by the investigator/co-investigator prior to all study specific procedure (including screening procedures). No subject will be entered into this clinical trial without having a signed written consent form.

6 MULTI-SITE RESEARCH

N/A

7 STUDY TIMELINES

15 participants from RPCI will be enrolled to the study over approximately 48 months. Patients will be followed for PFS and survival for at least an additional 12 months.

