8.3 Exploratory Endpoints

- Median progression free survival by RECIST v1.1
- Median overall survival

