9.3 Follow-up Phase

Patients will be seen for an end of treatment visit to review adverse events, clinical outcome of therapy. If stable disease/response is demonstrated during repeat CT imaging, patients will continue in follow-up with CT imaging every 8 weeks until progression, clinical deterioration or withdrawal from the study. If in the clinical judgement of the treating team, it is in the best interest of the patient to pursue another therapeutic option, the patient will come off study and CT imaging will be obtained only as per SOC/protocol. 12 months of survival follow-up will be pursued by chart audit or if necessary phone contact. If the patient comes off study during the follow-up period to start a new treatment, the new treatment information will be captured in the database.

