11.1.1 Screening (performed between days -14 through day -1 unless otherwise specified)

- Recording of concomitant medications
- Medical and Surgical History
- Complete Physical Exam including height and weight
- Vital Signs
- ECOG Performance Status Assessment
- Hematology
- Chemistry
- CEA Level
- ANA testing
- Serum HCG pregnancy testing (within 7 days of Day 1 in women of child-bearing potential only)
- CT and/or MRI (within 28 days of start of treatment)
- EKG
- Liver Biopsy

11.1.2 Evaluations Performed on day 1 of each treatment week (day 1, 8, 15):

- Recording of concomitant medications
- Recording of Adverse Events
- Targeted Physical Exam including weight
- Vital Signs (temperature, blood pressure, pulse rate and respiratory rate) will be performed pre- treatment and at 30 and 60 minutes post rintatolimod
(± 5 minutes).
- ECOG Performance Status Assessment
- Hematology
- Chemistry
- Chemokine Modulating regimen
- Blood (60cc) for correlative studies on Day 1 and Day 15 only (within 1 hour after end of infusion treatment)

PROTOCOL TITLE: Phase 2A Study Evaluating a Chemokine-Modulatory Regimen in Patients with Colorectal Cancer Metastatic to the Liver

11.1.3 Evaluations Performed on days 2 and 3 of each treatment week(days 2,3, 9, 10, 16, 17):

- Recording of concomitant medications
- Recording of Adverse Events
- Vital Signs (temperature, blood pressure, pulse rate and respiratory rate) will be performed pre-treatment and at 30 and 60 minutes post rintatolimod (\pm 5 minutes).
- Chemokine Modulating regimen
- Blood (60cc) for correlative studies on Day 3 only (within 1 hour after end of infusion treatment)

11.1.4 Evaluations Performed on Day 20 (+/- 2 days):

- Recording of Adverse Events
- Liver Biopsy

11.1.5 End of Treatment Visit on Day 29 (+/- 10 days):

- Recording of concomitant medications
- Recording of Adverse Events
- Targeted Physical Exam including weight
- Vital Signs
- ECOG Performance Status
- Hematology
- Chemistry

NOTE: In the event patient cannot tolerate treatment with all 9 days of treatment, then Blood 60cc for correlative will be collected at time that the patient recovers from toxicities (ideally within 1 week of the last infusion). Liver biopsy will also be collected provided there is not an overriding safety concern for the patient.

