11.1.6 Follow-up (patients will be followed for 12 months after EOT visit)

- Survival status (phone contact/chart review is acceptable)
- CT scan and/or MRI: to be performed at day 46 (\pm 3 days). If reassessment scan shows stable disease/response, patients will continue in follow-up with CT imaging every 8 weeks until progression, clinical deterioration or withdrawal from study. If in the clinical judgment of the treating team, it is in the best interest of the patient to pursue another therapeutic option, the patient will come off study and CT imaging will be obtained only as SOC/protocol. In this instance, review of the subsequent disease assessment study will be requested for determination of RECIST parameters.

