2. At each time point, Physical exam to include assessment of Head/Ears/Eyes/Nose/Throat (HEENT), Skin, Chest/Lungs, Heart, Neck/lymph nodes, Abdomen including liver/spleen, Extremities and weight. Height to be collected at screening only. Physical exam does not need to be repeated on Day 1 if performed within 3 days prior to Day 1.

3. CBC with auto differential.

4. Glucose, BUN, creatinine, sodium, potassium, chloride, CO₂, calcium, total protein, albumin, alkaline phosphatase, AST, ALT, total bilirubin, amylase, lipase.

5. Within 7 days of Day 1 and as clinically indicated once on treatment in women of child-bearing potential only.

6. Blood (60cc) for in vitro assays will be drawn as outlined in section 11.2.

6^a. Day 3 only within 1 hour after end of infusion

7. Within 28 days prior to Day 1.

8. Vital Signs (blood pressure, pulse, respiratory rate and temperature) will be obtained at screening and end of treatment visits. On dosing days, vital signs will be obtained pre-treatment, 30 and 60 minutes post Rintatolimod (± 5 minutes).

9. Patients will be followed for survival status for 12 months after end of treatment visit. Phone contact/chart review is acceptable.

10. Restaging imaging CT/MRI to be performed on day 46 ± 3 days. If this scan demonstrates stable disease/response, patients will continue in follow-up with CT imaging every 8 weeks until progression, clinical deterioration or withdrawal from study. If in the clinical judgement of the treating team, it is in the best interest of the patient to pursue another therapeutic option, the patient will come off study and CT imaging will be obtained only as SOC/protocol.

11. Once every 3 months for up to 12 months after EOT visit to ascertain survival – both chart review and/or phone contact are acceptable

PROTOCOL TITLE: Phase 2A Study Evaluating a Chemokine-Modulatory Regimen in Patients with Colorectal Cancer Metastatic to the Liver

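### Survival follow-up is a 12-month minimum in Section 7 but a 12-month maximum in Appendix F; under the calendar, median OS is at risk if the true median is near or above a year

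*Combined protocol and SAP*

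**What the plan says.** The length of survival follow-up is stated in five places:

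- Section 7, after giving 15 participants and about 48 months of enrolment: "Patients will be followed for PFS and survival for at least an additional 12 months". This is a minimum, with no start point.
- Section 9.3: "12 months of survival follow-up will be pursued by chart audit or if necessary phone contact". This is a duration, with no start point.
- Heading of Section 11.1.6: "patients will be followed for 12 months after EOT visit".
- Appendix F, footnote 9: "Patients will be followed for survival status for 12 months after end of treatment visit".
- Appendix F, footnote 11: "Once every 3 months for up to 12 months after EOT visit to ascertain survival". This is the only one of the five worded as a maximum.

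Section 11.1.5 places the EOT visit at Day 29, plus or minus 10 days. Section 8.3 lists "Median overall survival" among the exploratory endpoints. Section 19.3 measures OS from the start of treatment to death or last follow-up and summarises it by Kaplan-Meier. The plan gives no assumed median OS, no target number of deaths, no survival data cut-off and no rule for reporting a median that is not reached.

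**The concern.** A floor and a ceiling of the same length agree only if every patient is followed for exactly 12 months. Coming straight after the 48-month accrual, the Section 7 sentence most naturally means follow-up beyond the end of enrolment. On that reading an early enrolee would be followed for several years. The calendar, which site staff work from, ends survival contact one year after EOT for everyone.

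Under the calendar all survivors are censored at nearly the same point, about 13 months after starting treatment. Kaplan-Meier gives a median only if the curve falls to one half by then. If the true median is close to a year or longer, the trial may finish without the summary that Section 8.3 names, although later survival status could have been had from the chart. In a 15-patient dataset, status that is not collected is a real loss.

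**Working it through.** **The plan's own figure.** There is none for OS. The only stated design figure is 90% power for the primary test in Section 19.2 (n = 12, 0.77 SD, one-sided 0.1). It reproduces: noncentral t with 11 df and noncentrality 0.77 × √12 gives 0.900. It does not depend on OS follow-up.

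**Inputs from the documents.** 15 treated patients over about 48 months (Section 7); EOT at Day 29 ± 10 (Section 11.1.5); follow-up to 12 months after EOT (Section 11.1.6 and Appendix F); OS counted from start of treatment (Section 19.3).

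**Assumptions.** Exponential survival; no loss before the cap; 30.44 days per month. Earlier loss would lower the chances below.

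**Step 1: where the cap falls.** 12 + 29/30.44 = 12.95 months from start of treatment. At the edges of the EOT window it is 12 + 19/30.44 = 12.6 and 12 + 39/30.44 = 13.3 months.

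**Step 2: deaths needed.** With all 15 followed to the cap, the curve is at 8/15 = .533 after 7 deaths and 7/15 = .467 after 8. The median needs at least 8 deaths.

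**Step 3: chance of reaching it.** For a true median of m months, the probability of death by the cap is p = 1 − 2^(−12.95/m), and the chance of reaching the median is P(Binomial(15, p) ≥ 8). At m = 12, p = .527, expected deaths are 15 × .527 = 7.9, and the chance is .58.

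| True median (months) | p | Median reached, calendar cap | Median reached, open follow-up |
|---|---|---|---|
| 4 | .894 | 1.00 | 1.00 |
| 6 | .776 | .99 | 1.00 |
| 8 | .674 | .92 | 1.00 |
| 10 | .593 | .77 | 1.00 |
| 12 | .527 | .58 | 1.00 |
| 14 | .473 | .42 | 1.00 |
| 18 | .393 | .20 | .99 |
| 24 | .312 | .06 | about .93 |
| 30 | .259 | .02 | about .84 |

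The last column is simulated: uniform accrual over 48 months, with everyone followed until the last enrolled patient is 12 months past EOT. If each patient instead has between 12 and 60 months, the last two entries are .95 and .87. Under the cap, the chance falls to about one half at a true median of 13 months.

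**Step 4: precision.** The plan specifies no interval for median OS. With a log-log 95% interval as an assumption, simulation under the cap shows the upper limit reached in about 79% of trials at a true median of 6 months, 44% at 8 and 9% at 12. With 12 to 60 months of follow-up per patient it is reached in more than 99% at 6 and 8 months and about 94% at 12.

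**Which row applies.** The documents do not say. Section 2.1 gives medians of 4–12 months for untreated hepatic metastases, 8–14 months on 5-FU regimens, up to 24 months with oxaliplatin or irinotecan added, and about 30 months with biologic agents as well. Inclusion criterion 3 admits patients who have had, cannot have or refuse the standard drugs, so none of these is a direct benchmark.

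**The case against.** The strongest reply is that the texts can be reconciled as they stand. Section 7 is a study-level timeline, and 12 months per patient literally meets a 12-month minimum. A fixed one-year follow-up is a legitimate choice for a small single-arm study sized on a biopsy endpoint, and no hypothesis, sample size or stopping rule depends on OS. This stands in part: it makes the matter minor. It does not settle which rule a site should follow, because Section 7 has no start point, footnote 11 forbids what Section 7 appears to invite, and no cut-off is given.

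Several stronger readings are tempting but not supported:

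- *Every operational section imposes a maximum at 12 months after EOT.* Section 9.3 names neither EOT nor a ceiling, Section 11.1.6 and footnote 9 give a duration, and only footnote 11 sets an upper bound.
- *All contact stops at one year.* CT every 8 weeks for patients with stable disease or response runs until progression, clinical deterioration or withdrawal, with no month limit attached to that rule. The heading of Section 11.1.6 could be read as limiting it, so this point is unclear.
- *Median OS will probably not be estimable.* That needs a true median above about 13 months. At 9 months or less the chance of reaching it is .85 or more, and across the 4–12 month untreated range it stays above one half.
- *The OS analysis would yield nothing.* The Kaplan-Meier curve and 12-month survival would still be available, and a median not reached is itself a reportable result.
- *Amendment 8 makes failure likelier.* The phrase about earlier-line patients is a parenthesis in the interim-analysis text of Section 19.3. Criterion 3 still requires prior treatment, contra-indication or refusal, and no survival shift is quantified.

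**Conclusion.** The inconsistency is real and minor. The five statements differ on start point and on whether 12 months is a floor or a ceiling. Under the calendar the observation window for OS closes 12.6 to 13.3 months after start of treatment. The cost depends on a median the documents do not supply: little at 8 months or below, close to an even chance at 12 to 14 months, and failure in about four trials in five at 18 months. A missing upper confidence limit is a more frequent consequence and already appears at shorter medians. All of this rests on exponential survival, 15 patients and no loss before the cap. The primary analysis and sample size are not touched.

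**What to change.** Reconcile Sections 7, 9.3 and 11.1.6 and Appendix F footnotes 9 and 11 to one start point and one survival data cut-off. The preferred wording collects survival status by chart review or phone every 3 months until death or until the last enrolled patient is 12 months past EOT. State in Section 19.3 that a median not reached will be reported as such, with the Kaplan-Meier estimate at 12 months. In the same edit, correct the calendar's adverse-event row at Day 46, which carries footnote 9 although that footnote concerns survival.

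Under the assumptions above this raises the chance of reaching the median to about .99 or more for true medians up to 18 months, about .93 at 24 and about .84 at 30. The cost is protocol wording and some extra chart reviews or calls for early enrolees, by methods the protocol already accepts. No visits or scans are added. If the sponsor prefers a fixed year per patient, Section 7 should say so and 12-month survival should be pre-specified as the OS summary.
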